NGM282 has recently been evaluated in 80 patients with T2D, many of whom have presumptive NASH ([Study 13-0102](#)). NGM282 was administered for 28 consecutive days in patients randomized into one of the four treatment conditions (NGM282 at doses of 2, 5, or 10 mg; or placebo). Dose-dependent improvement in insulin sensitivity and body weight, as well as decreases in triglycerides and ALT, were observed compared to placebo as well as a trend to a decrease in fasting blood glucose and a slight increase in HDL. Total cholesterol and low-density lipoprotein (LDL) were modestly increased with NGM282 at Day 28. This increase appears to represent an acute change at Day 14, followed by a decrease from Day 14 to Day 28, consistent with a mitigation of this rise over time. C4 was suppressed by > 95% in subjects treated with the 2- and 5-mg doses. NGM282 was well tolerated with no SAEs or safety signals observed during the study. Mild to moderate GI symptoms (nausea, loose stools) as well as mild ISRs were the most frequently reported AEs, both of which were seen more frequently at the higher doses. In general, NGM282 was well tolerated in a population with characteristics similar to those in patients with NASH.

Based on the identified activities in animal models as well as the PK and favorable safety and tolerability profiles in normal volunteers and T2D patients, NGM282 represents a potentially important therapeutic option for the treatment of NASH through enhanced FGF19 signaling.

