3.5. DETERMINATION OF SAMPLE SIZE

[REDACTED]

Amendment Final V 2.0

[REDACTED] the assumptions of calculated sample-size estimates for 24-week efficacy used an NGM282 response of 50% versus 15% for placebo utilizing 80% power and alpha=0.05 with a 2:1 randomization scheme. Assuming a 15% drop-out rate, the planned sample size of 50 NGM282-treated subjects and 25 placebo subjects is sufficient to evaluate efficacy and support powering estimates for late-stage clinical trials.

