6. GENERAL ASPECTS FOR STATISTICAL ANALYSIS

6.1. GENERAL METHODS

Unless otherwise specified, for numeric data, descriptive statistics will include the number of subjects with data to be summarized (n), mean, standard deviation (SD), median, minimum (min), and maximum (max). The same number of decimal places as used in the raw data will be presented when reporting min and max, 1 decimal place more than in the raw data will be presented when reporting mean and median, and SD. If the raw data have 3 decimals or more, 3 decimals will be presented for the mean, median, min and max, and SD.

All categorical/qualitative data will be presented using frequency counts and percentages. All percentages will be rounded to 1 decimal point, with the denominator being the number of subjects in the relevant population, unless otherwise stated. Percentages equal to 100 will be presented as 100%; percentages will not be presented for zero frequencies but the categories whose counts are zero will be displayed for the sake of completeness.

Unless otherwise specified, all the tables will be summarized by treatment group (and overall, if applicable). All the listings will be sorted by treatment group, subject number and assessment date/time.

All confidence intervals (CIs) will be two-sided and will use 95% confidence levels. Any analyses requiring significance testing will use a two-sided test at the 5% significance level, unless otherwise specified.

In general, only data from nominal scheduled visits will be presented in the summary tables and figures unless otherwise specified. Data from unscheduled visits will not be summarized but will be presented in the data listings.

All analyses and outputs will be generated using SAS® version 9.4 (or higher).

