8.2. SECONDARY EFFICACY/PD ENDPOINT(S) AND ANALYSES

The main analysis population for secondary efficacy endpoints is the Efficacy Population. The analysis will also be repeated for the Per Protocol population and for subjects who completed their Week 24 assessment (completers) only.

8.2.1. The actual and percentage change from baseline in liver fat content by Magnetic Resonance Imaging-proton Density Fat Fraction. MRI-PDFF at Weeks 6, 12, 24, and 30

The observed values and changes from baseline will be summarized at Weeks 6, 12, 24, and 30, by NGM282 treatment group and fibrosis stage. The actual change and percentage change in absolute liver fat content from baseline to Week 6, Week 12, Week 24 and Week 30 will be compared between treatment groups using an analysis of covariance (ANCOVA) model with treatment group and fibrosis stage at baseline as cofactors and baseline endpoint and baseline ALT as covariates. Least square means with standard errors (SE), differences in least square means with SE, 95% CIs for the difference in least square means, and corresponding p-values will be presented.

The assumptions of normality will be evaluated. If the assumptions of normality are not satisfied, a rank ANCOVA method will be performed in addition to the parametric model.

The rank ANCOVA is a non-parametric statistical method described in Stokes, Davis, and Koch, 2000. It can be considered as an extension to the Wilcoxon rank-sum test with the ability to adjust for covariates and cofactors in the model. The mean, median and p-value for the actual change will be presented.

8.2.2. The percentage of normalization in absolute liver fat content at Week 24

Normal liver fat content normalization will be defined as $\leq 5.0\%$. Percent of subjects with normalized liver fat content will be presented by treatment group and fibrosis stage and will be analyzed through a chi-square test. The difference between proportions observed in each treatment group, along with 95% CIs for the difference between proportions, will be presented for all pairwise comparisons of treatment

Amendment Final V 2.0

groups. Fisher exact test will be used if 50% of the cells have expected counts less than 5.

8.2.3. The percentage of responders (based on a liver fat content decrease $\geq 5\%$, and relative decrease $\geq 30\%$)

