The percentage of responders will be analyzed through a chi-square test. The difference between proportions observed in each treatment group, along with 95% CIs for the difference between proportions, will be presented for all pairwise comparisons of treatment groups. Fisher exact test will be used if 50% of the cells have expected counts less than 5.

[REDACTED]

[REDACTED]

[REDACTED]

8.2.4. The actual and percentage changes from baseline by Week 24 of AST, ALT, bilirubin (total, direct), triglycerides and GGT.

The actual and percentage changes from baseline will be summarized by treatment group. An ANCOVA model as stated in 8.2.1 will be used to compare between treatment groups.

In addition, the percentage of subjects with AST, ALT, Total Bilirubin, Direct Bilirubin, Triglycerides, and GGT lab measurements within the normal range will be summarized by lab parameter, treatment group and visit. All pairwise treatment group comparisons of the proportion of subjects within the normal range will be tested using a chi-square test. Fisher exact test will be used if 50% of the cells have expected counts less than 5.

[REDACTED]

8.2.5. The actual and percentage changes from baseline at Week 24 and EOS of the following parameters: Total cholesterol, HDL-cholesterol, LDL-cholesterol, and lipoprotein particles.

The actual and percentage changes from baseline will be summarized by treatment group and fibrosis stage. ANCOVA model as stated in 8.2.1 will be used to compare between treatment groups. The ANCOVA model as stated in 8.2.1 will be used to compare the two treatment groups.

Amendment Final V 2.0

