8.2.7. Other Secondary Endpoints

The actual and percentage changes from Baseline at Week 24 of the following parameters: [REDACTED], PRO-C3, ELF score, Fasting blood glucose, insulin levels, HbA1c, [REDACTED] [REDACTED], and HOMA-IR, Body weight, BMI, and waist circumference, C4 and serum bile acids, Bile-mediated absorption as measured by vitamin D, INR, and fecal fat content.

The actual and percentage changes from baseline will be summarized by NGM282 treatment group. ANCOVA model as stated in 8.2.1 will be used to compare between treatment groups.

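### SAP 8.2.4 and 8.2.7: the single-variance ANCOVA on percent change at 2:1 allocation gives 95% CIs that are too narrow for strongly reduced markers such as C4

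*SAP*

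**What the plan says.** SAP 6.2.3 defines percent change arithmetically, as the difference divided by baseline. SAP 8.2.1 sets out an ANCOVA with treatment and baseline fibrosis stage as factors, and the baseline value and baseline ALT as covariates. It reports least-squares mean differences, 95% CIs and p-values.

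SAP 8.2.4 extends this model to actual and percent change in AST, ALT, bilirubin, triglycerides and GGT: "An ANCOVA model as stated in 8.2.1 will be used to compare between treatment groups". SAP 8.2.7 does so for C4, serum bile acids, PRO-C3, insulin, HOMA-IR and others: "ANCOVA model as stated in 8.2.1 will be used to compare between treatment groups".

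The visible text contains no log transformation, robust standard error or arm-specific variance. The only assumption that SAP 8.2.1 checks is normality. If it fails, "a rank ANCOVA method will be performed in addition to the parametric model", and the stated output is a mean, a median and a p-value for the actual change. On intervals, SAP 6.1 says "All confidence intervals (CIs) will be two-sided and will use 95% confidence levels". Allocation is 2:1 (SAP 3.5).

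**The concern.** A drug that multiplies a marker by a small factor also multiplies the spread of its percent change by that factor. Percent change cannot fall below -100%, so under heavy suppression the active arm bunches near that floor while the placebo arm keeps its full spread. Two thirds of the subjects are in the active arm, so a pooled variance is weighted towards the small one. The uncertainty of the difference, however, comes mostly from the small placebo arm.

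The result would be published intervals labelled 95% that cover less than that. It would happen where the drug works best, on the pharmacodynamic markers used to show target engagement.

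**Working it through.** **Inputs from the documents.** Two-sided 5% level and 95% CIs (SAP 6.1). The sample size "used an NGM282 response of 50% versus 15% for placebo utilizing 80% power and alpha=0.05 with a 2:1 randomization scheme" (SAP 3.5). The same section adds 15% for dropout, giving 50 active and 25 placebo. For C4, Protocol 5.1.3 reports "C4 was suppressed by > 95% in subjects treated with the 2- and 5-mg doses", in type 2 diabetes over 28 days. For ALT, Protocol 5.7 gives only a normalization rate (over 50% of subjects by Week 12 in the double-blind cohort).

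**Not in the documents, so assumed.** The distribution, the SDs and the 1 mg percent effects of every marker concerned.

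**Step 1: evaluable numbers.** The usual two-proportion formula without continuity correction, 15% v 50% at 2:1, with pooled proportion (0.15 + 2 x 0.50)/3 = 0.383:

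placebo n = [1.96 x sqrt(1.5 x 0.383 x 0.617) + 0.842 x sqrt(0.25/2 + 0.1275)]^2 / 0.35^2 = 20.6, so 21 placebo and 42 active. Dividing by 0.85 gives 24.7 and 49.4, that is 25 and 50. The plan's 75 reproduces, and 42:21 is the evaluable split.

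**Step 2: large-sample coverage.** Let r be the SD of percent change in the active arm divided by that in placebo. In units of (placebo variance)/42:

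- variance that the model reports: 2r^2 + 1
- true variance of the difference: r^2 + 2
- coverage = 2 x Phi(1.96 x sqrt[(2r^2 + 1)/(r^2 + 2)]) - 1

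If the drug multiplies the marker by (1 - f) and the log-scale SD is equal in both arms, then r = 1 - f.

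| Fall f | r | reported SE / true SE | coverage |
|---|---|---|---|
| limit | 0 | 0.707 | 83.4% |
| 95% | 0.05 | 0.708 | 83.5% |
| 70% | 0.30 | 0.751 | 85.9% |
| 50% | 0.50 | 0.816 | 89.0% |
| 30% | 0.70 | 0.892 | 92.0% |
| none | 1 | 1 | 95.0% |

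Coverage drops below 90% only when r is under about 0.56.

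**Step 3: simulation of the SAP model** (treatment, fibrosis stage, baseline, baseline ALT) on arithmetic percent change of lognormal markers with equal log SD in both arms, at 42:21 and 50:25, 4,000 trials per setting:

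- C4-like, log SD about 0.5: about 80-85% for falls of 70-95%. At a 95% fall, 80-82% for log SD 0.4-0.6 and 74-78% for 0.8-1.0.
- ALT-like, log SD 0.2-0.5: 88-89% at a 50% fall, 89-91% at 40%, 91-93% at 30%.
- Triglyceride-like: 91-92% at a 35% fall, 92-93% at 25%, 94-95% at 15%, 95-96% with no effect.

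**Step 4: unequal log SDs.** With a 90-95% fall and active log SD about twice placebo, coverage is still about 83-87%. With a 50% fall it depends on direction: 94.5% if the active SD is larger (0.6 v 0.4), 84% if it is smaller (0.25 v 0.4).

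**Step 5: the remedy.** ANCOVA on the log ratio covers 94-96% when log SDs are equal, but about 89-98% when they differ by arm. Log ratio with HC3 standard errors gave about 95-96% throughout. HC3 on arithmetic percent change gave 94-96% for ALT- and triglyceride-like markers but only 85-94% for C4-like ones.

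**The case against.** The strongest reply is that no coverage figure can be derived from the documents. They state no SD for these markers, and the C4 figure comes from other doses, another population and 28 days. That stands: only the 83% limit follows from the design, and the rest is conditional on assumptions. It does not remove the problem, because Step 4 shows the shortfall persists for a strongly suppressed marker even when the active arm is more variable on the log scale. For a 50% fall, the reply can succeed outright.

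Second, the Protocol (Section 12 and 12.9.2) calls for non-parametric methods when distributional requirements fail, and parts of SAP 8.2.4 and Section 14 are redacted. Both are true. But as visible, the SAP looks only at normality, adds the rank analysis beside the parametric one and gives it no interval. The parametric CI is still reported.

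Third, these are secondary endpoints with no stated decision rule attached to their intervals. That limits the consequence; the sample size is untouched.

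Stronger readings that a reader might infer, and that are not supported:

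- That every skewed marker, triglycerides included, is covered only 80-90% of the time. For falls up to about 35%, triglyceride-like coverage is 91% or more.
- That skewness itself is the cause, or that false positives rise. With no effect coverage is about 95%, so the test of no effect keeps its 5% level.
- That taking logs is enough. It is not if log variances differ by arm. With half the limit substituted and 82% of active C4 values below quantification (assumed), log-scale coverage was 65%; at 50% below it was about 94%.

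**Conclusion.** The point holds for markers that the drug reduces strongly. With 2:1 allocation and one residual variance, the planned 95% CI for the difference in percent change is too narrow. The limit is 83% coverage; about 80-85% is plausible for a C4-like fall of 70-95% and 88-89% at a 50% fall. Markers with modest changes are little affected.

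The direction follows from the design. The percentages rest on lognormal markers, similar log SDs of about 0.5 in the two arms and about 42:21 evaluable subjects. Whether 1 mg suppresses C4 enough to reach the lower figures is not stated in the documents. This is a correction to the error bars of secondary endpoints that should be made; it does not bear on the sample size.

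**What to change.** In SAP 8.2.4 and 8.2.7, for right-skewed markers expected to change proportionally (C4, bile acids, ALT, AST, GGT, triglycerides, PRO-C3, insulin, HOMA-IR):

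- Analyse log(Week 24/baseline) with log(baseline), fibrosis stage and the other planned covariates, using HC3 or arm-specific variances.
- Report geometric-mean ratios to placebo with 95% CIs.
- State the rule for values below quantification, with a sensitivity analysis for C4.
- Keep arithmetic actual and percent change as descriptive summaries. If their model comparison is retained, use robust standard errors there too, noting from Step 5 that this repairs C4-like markers only in part.
- Record the change in SAP Section 11, which now lists none. The Protocol (12.9.3 and Synopsis) specifies ANCOVA on percent change, so this is a departure from it.

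Cost: SAP wording, one more programming step, and a change in what is estimated, from a difference in mean percent change to a ratio of geometric means.

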8.3. EXPLORATORY EFFICACY/PD ENDPOINT(S) AND ANALYSES

[REDACTED]

[REDACTED]

[REDACTED]

[REDACTED]

[REDACTED]

[REDACTED]

[REDACTED]

[REDACTED]

Amendment Final V 2.0

9. SAFETY

9.1. EXTENT OF EXPOSURE

Treatment exposure will be based on the Safety Population. Individual data listings for treatment exposure will be presented for each subject. Treatment exposure will be summarized by assessing the duration of exposure and compliance. Treatment compliance is defined as the number doses administered/number of doses prescribed per protocol during the time the subject was on study.

9.2. ADVERSE EVENTS

AEs, including serious AEs, will be coded using the MedDRA Version 18.0. The number and percentage of subjects experiencing an AE will be summarized for each system organ class (SOC) and preferred term (PT) by treatment group. In addition, AEs will be tabulated according to severity, causality, and relation to the study drug (both NGM and Rosuvastatin).

All AE summaries will be restricted to Treatment Emergent Adverse Events (TEAEs) only. TEAEs are defined as AEs that commence on or after the date of first study drug administration. AEs without an onset date or time will be defined as treatment emergent, except if an incomplete date (e.g., month and year) clearly indicates that the event started prior to the start of first administration of study drug or if the AE stop date indicates that the event started or stopped prior to the start of first administration of study drug. Please refer to Section 6.3 for determination of TEAEs for completely or partially missing dates.

The intensity of AEs is rated by CTCAE v4.03. For both NGM282 and Rosuvastatin, adverse events might be not related, possibly related, probably related and definitely related to these study drugs.

For the summaries of AEs, subjects who experience the same AE (in terms of the MedDRA preferred term) more than once will be counted only once for that event. Separate summaries will be provided for AEs by intensity, causality, and relationship to study drug. For summaries by SOC, PT, and maximum intensity, a subject is counted once at the highest intensity level for which the event occurred at the SOC level and the highest intensity level for each unique PT within that SOC level. Therefore, subjects may only contribute once to each PT and once to each SOC level. Summaries by relatedness would be handled similar to the summaries by intensity.

The summaries presenting frequency of AE by SOC and PT will be ordered by overall descending frequency of SOC and then, within a SOC, by overall descending frequency of PT.

The following tables will be summarized for adverse events.

Amendment Final V 2.0

- An overall summary of the number and percentage of subjects reporting any TEAEs, serious TEAEs, NGM282-related TEAEs, Rosuvastatin-related TEAEs, TEAEs leading to withdrawal and TEAEs leading to death.
- TEAEs overall and by system organ class and preferred term
- TEAEs by CTCAE grade, overall and by system organ class and preferred term.
- TEAEs of CTCAE grade 3 or higher, overall and by system organ class and preferred term.
- TEAEs leading to withdrawal, overall and by system organ class and preferred term
- Serious TEAEs, overall and by system organ class and preferred term
NGM282-related
- NGM282-related TEAEs overall and by system organ class and preferred term
- TEAEs by maximum relationship to NGM282, overall and by system organ class and preferred term
- NGM282-related TEAEs leading to withdrawal, overall and by system organ class and preferred term
- NGM282-related Serious TEAEs, overall and by system organ class and preferred term Rosuvastatin-related
- Rosuvastatin-related TEAEs overall and by system organ class and preferred term
- TEAEs by maximum relationship to Rosuvastatin, overall and by system organ class and preferred term
- Rosuvastatin-related Serious TEAEs, overall and by system organ class and preferred term
- Rosuvastatin-related TEAEs leading to withdrawal, overall and by system organ class and preferred term

For the rosuvastatin-related summary tables, only subjects who received rosuvastatin will be included. All AEs will be provided in listings regardless of TEAEs or not. All Serious AEs and AEs leading to study drug withdrawal and death will be provided in separate listings.

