d A liver biopsy result is required at Screening and at Week 24. A historical biopsy within 3 months of Screening may be used instead of undergoing a new procedure. Week 24 biopsy should be obtained before the last dose of NGM282 or placebo with a visit window of -7 days and +3 days

e Lab results for ALT, AST, Total Cholesterol, LDL, HDL and triglycerides are blinded to site from Week 2 onward. Patient reports to clinic fasted on Day 1 or is rescheduled. All other clinic visits, chemistries and lipid panel will need to be retested if not fasted.

f A serum pregnancy test will be performed on all female subjects of child bearing potential at Screening, Week 24, and Week 30. A urine pregnancy test will be performed on all female subjects of child bearing potential at Day 1 (pre-dose).

g PK blood samples will be collected in all subjects before dosing themselves in the clinic (pre-dose) and at 2 hours (±20 mins) post-dose at Day 1, Week 12, and Week 24.

h Rosuvastatin will be dispensed at Weeks 2, 4, 8, 12 and 18 visits and subjects will be provided further dosing instruction based on their LDL-C levels and whether they are statin-naïve versus statin experienced. Subjects on a statin at screening will be dispensed additional rosuvastatin at Week 24 and continue through Week 30.

i Compliance with Rosuvastatin will be assessed at Week 30 for statin-experienced subjects only

j Baseline ALT reported result calculated using the median of the Screening and Day 1 value

k Adverse events will be monitored and recorded from patient signing informed consent through follow-up.

l Subjects will be instructed to self-inject NGM282 or placebo as close to the same time as possible each day in the abdomen and administer the next dose the following morning. Subjects will not self-inject NGM282 at home on clinic visit days.

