### **9.6.3 Week 2 Procedures**

Subjects will report to clinic fasted and not dosed with NGM282. The following procedures will be performed:

Pre-dose:

- Measure vital signs (including temperature, respiratory rate, and seated blood pressure and pulse).

- Obtain blood for 10-hour fasted clinical laboratory samples (if not fasted, chemistries and lipid panel will need to be retested)
  - Results are blinded for ALT, AST, Total Cholesterol, LDL, HDL and triglycerides
- Record concomitant medications.
- Record new and/or changes to AEs.

In-clinic dosing and dispensing:

- Collect old NGM282 study-drug kit/diary and conduct reconciliation.
- Dispense new NGM282 study-drug kits (2) and diary.
- Dispense rosuvastatin medication/diary
- Oversee subject's NGM282 study-drug self-administration (from new kit).
- Perform LISSA evaluation.

Before clinic discharge:

- Remind subject to bring study drug kits/diary and to not self-inject NGM282 at home on clinic visit days.
- Schedule Week 4 visit and remind subject for home dosing to administer NGM282 or placebo as close as possible to the same time each day

Lipid-Lowering Therapy Assessment:

- NGM Medical Monitor/designee will evaluate LDL-C level as outlined in [Section 10.4](#) and inform site to:
  - Start or not start rosuvastatin therapy
  - Continue with current therapy
  - Switch to rosuvastatin therapy
- The site will then contact the subject with further instructions

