### **12.10.1 Adverse Events**

AEs, including serious AEs, will be coded using the MedDRA. The number and percentage of subjects experiencing an AE will be summarized for each system organ class (SOC) and preferred term (PT) by treatment group. In addition, AEs will be tabulated according to intensity, causality, and relation to the study drug. Individual data listings for AEs will be presented for each subject.

All AE summaries will be restricted to TEAEs only. TEAEs are defined as AEs that commence on or after the time of start of first study-drug administration. AEs without an onset date or time will be defined as treatment emergent, except if an incomplete date (e.g., month and year) clearly indicates that the event started prior to the start of first administration of study drug or if the AE stop date indicates that the event started or stopped prior to the start of first administration of study drug.

For the summaries of AEs, subjects who experience the same AE (in terms of the MedDRA preferred term) more than once will be counted only once for that event. Separate summaries will be provided for AEs by intensity, causality, and relationship to study drug.

All AEs will be listed. SAEs will be summarized and listed.

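### An adverse event already open at first dose that worsens on study drug under its original onset date would be left out of every by-arm AE table

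*SAP*

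**What the plan says.** The rule for the tables is in SAP 9.2: "All AE summaries will be restricted to Treatment Emergent Adverse Events (TEAEs) only", and "TEAEs are defined as AEs that commence on or after the date of first study drug administration". Every AE table named there is a TEAE table. Two examples are "Serious TEAEs, overall and by system organ class and preferred term" and "TEAEs of CTCAE grade 3 or higher, overall and by system organ class and preferred term". Events that are not treatment-emergent go only to listings: "All AEs will be provided in listings regardless of TEAEs or not".

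Protocol 12.10.1 also defines the term by onset, but by clock time: "TEAEs are defined as AEs that commence on or after the time of start of first study-drug administration". Protocol 11.1 has a third wording, which depends on the AE being reported following a dose and does not mention onset.

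Collection begins well before dosing. Footnote k to protocol Table 4 reads: "Adverse events will be monitored and recorded from patient signing informed consent through follow-up". Screening lasts 28 days and can be extended to 42 with Medical Monitor approval (protocol 9.5). From Day 1 through Week 30 the site instruction is "Record new and/or changes to AEs" (protocol 9.6.2 to 9.6.10).

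**The concern.** A definition of treatment-emergent normally covers two cases: an event that starts after first dose, and an event already present that gets worse after first dose. These documents cover only the first. The second can occur in this cohort, because AEs are collected from consent and an event can be open when dosing starts.

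Safety and tolerability is a stated secondary objective. Gastrointestinal symptoms are among the most frequent AEs reported with this drug (protocol 5.1.3), and less persistent gastrointestinal symptoms were part of the case for 1 mg (protocol 5.4). A symptom that was mild in screening and became severe or serious on drug belongs in the comparison by arm. Under the stated rule it may not get there. With 50 active and 25 placebo subjects planned, the Grade 3 or higher, serious and withdrawal rows may hold few events, so a single omission would be noticeable.

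**Working it through.** The plan gives no figure to reproduce. The check is to apply the written rules to the cases that can arise.

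**Does any text add worsening?** SAP 9.2 and protocol 12.10.1 use onset only. SAP 6.3 deals with missing and partial dates and has no severity criterion. Protocol 11.1 does not mention worsening. SAP 11 records no change from the protocol.

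**Does any text say how a rise in grade is recorded?** The visit instruction mentions changes to AEs but does not say whether a change updates the existing record or opens a new one. No CRF completion guide is among the documents.

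**Applying the rules**

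| Case | Onset on record | In the by-arm AE tables (SAP 9.2)? |
|---|---|---|
| A. Grade 1 on Day -10, Grade 3 at Week 4, same record updated | Day -10 | No; listing only |
| B. Same event, new record opened at Week 4 | Week 4 | Yes |
| C. Condition held before consent (medical history) that worsens at Week 4 and is entered as an AE | Week 4 | Yes |
| D. Event starting on Day 1 before the first injection | Day 1 | Yes by date (SAP 9.2); no by time (protocol 12.10.1) |
| E. Symptom starting before dosing, start day missing, in the month of first dose and not shown by other data to be earlier | Set to first-dose date (SAP 6.3) | Yes |

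Case A is the gap. Cases B and C mark its limits. Case D shows that the date and time wordings give different answers. Case E shows an uneven result: a poorly dated pre-dose event can enter the tables, while an accurately dated one that worsens on drug does not.

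**Size.** The documents do not give the share of subjects with an AE open at Day 1, or the share of those that worsen. What can be computed is the effect of one omitted subject on a table row, assuming all 50 active and 25 placebo subjects are in the Safety Population:

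- active arm: 1/50 = 2.0 percentage points;
- placebo arm: 1/25 = 4.0 percentage points.

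For illustration only, assume that 10–20% of the 75 subjects have an AE open at Day 1 and that 10–20% of those worsen. That gives 75 × 0.10 × 0.10 = 0.75 to 75 × 0.20 × 0.20 = 3.0 subjects, counting worsening of any grade and cause. Both percentages are assumptions without a source in the documents.

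**The case against.** The best answer is that exclusion depends on recording practice. If sites log a worsening as a separate event, SAP 9.2 counts it. Protocol 11.1 includes deterioration in general condition among AEs, which would support doing so. SAP 9.2 also counts a subject once per preferred term at the highest grade, which fits several records of one term. The table index is redacted and the mock-ups are separate documents. This stands as a limit: the omission is conditional. It does not remove the point, because nothing requires the separate record.

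Much worsening also has another route. Liver enzymes, bilirubin, triglycerides, lipids and glycaemic measures are compared by arm with ANCOVA (SAP 8.2.4, 8.2.5, 8.2.7). Chemistry and hematology have shift tables (SAP 9.3). Injection-site reactions have their own tabulation by arm (SAP 9.6). All AEs are listed, with separate listings for serious AEs and for those leading to withdrawal or death, and listings are sorted by treatment group. This stands too. What remains is mainly symptomatic AEs, for which listings give no rates by arm.

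A reader might infer three stronger claims that the documents do not support:

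- That worsening of NASH patients' long-standing complaints disappears from the tables. Conditions held before consent are medical history, and their worsening can be entered as a new AE (case C).
- That worsening of existing complaints is a main way this drug's toxicity would appear. No section says so.
- That the study-stop trigger in protocol 7.1 would be undercounted. The SAP's table definition does not govern decisions made during conduct, and the wording in protocol 11.1 might take in a worsening reported on drug. The trigger also needs three or more related Grade 3 or 4 events of one CTCAE category, so a count of any worsening cannot be set against it.

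**Conclusion.** The point holds for the tables. As written, SAP 9.2 and protocol 12.10.1 omit from every by-arm AE summary an event that began in screening, was still open at Day 1, and worsened or became serious on drug under its original onset date. Such an event would be seen only in the listings, apart from any laboratory worsening shown in the laboratory outputs.

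This rests on two conditions: that the worsening is kept on the existing record, which the visit instruction allows, and that the unseen mock-ups follow the text of SAP 9.2. The number affected cannot be derived from the documents and is probably small. This is a correctable error in how safety is counted, not evidence that a safety signal would be lost. The three TEAE wordings are a separate inconsistency.

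**What to change.** 1. In SAP 9.2, for the safety tables, and in the matching text of protocol 12.10.1, define a TEAE as an AE with onset on or after first dose, or an AE with onset before first dose that rises in CTCAE grade or becomes serious on or after first dose.
2. Add a CRF completion instruction that such a worsening is entered as a new AE record with its own start date. Without a date for the rise in grade, the added clause cannot be programmed reliably. Subject counts are not inflated, because SAP 9.2 counts a subject once per preferred term.
3. Separately, reconcile the three wordings: reporting following a dose in protocol 11.1, time of first dose in protocol 12.10.1, and date of first dose in SAP 9.2. Protocol 7.1 and 8.2 use the same term, so they should state which definition they rely on. No change to the stopping or discontinuation rules is proposed here.

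The cost is one sentence in each document and one site instruction. AE counts may rise slightly in both arms.
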